This material is the property of the NYU School of Medicine and Langone Medical Center. Do not disclose or use except as authorized in writing by the study sponsor

List of Abbreviations

ASA	American Society of Anesthesiologist Score
VAS	Visual analog scale
TSA	Total Shoulder Arthroplasty
ISB	Interscalene Nerve Block
DVT	Deep vein thrombosis
ER	Emergency room
AE	Adverse event
SAE	Serious adverse event
IV	Intravenous
PO	Taken orally
PRN	Taken as needed
TID	Taken three times per day
Q4h	Taken every four hours
CI	Confidence interval
SD	Standard deviation; a parameter, which characterizes a population distribution
SE	Standard error
ANOVA	Analysis of variance; a linear model
NSAID	Non-steroidal anti-inflammatory drug

CONFIDENTIAL

This material is the property of the NYU School of Medicine and Langone Medical Center. Do not disclose or use except as authorized in writing by the study sponsor
Interventional Template Version: 28 APR 2017

Protocol Summary

Title	Liposomal Bupivacaine (Exparel®) Plus 0.5% Bupivacaine HCL versus 0.5 % Bupivacaine HCL for Interscalene Nerve Block (ISB) for patients undergoing Total Shoulder Arthroplasty (TSA)
Short Title	Understanding the effects of Exparel® on post-operative pain management and opioid utilization for patients undergoing TSA
Brief Summary	This is a phase IV, randomized, single-blind, single-center study comparing patient related outcomes such as postoperative pain and opioid usage for patients who receive ISB's containing liposomal bupivacaine (Exparel®) plus 0.5% bupivacaine HCL versus 0.5% bupivacaine HCL undergoing total shoulder arthroplasty.
Phase	Clinical study phase IV
Objectives	To compare opioid utilization and pain management of patients who receive Exparel in an ISB vs standard 0.5% bupivacaine HCL during the initial 72-hour post-operative period. Additionally, to understand the duration of block after addition of Exparel® to bupivacaine in an Interscalene block after TSA
Methodology	phase IV, randomized, single-blind, single-center study
Endpoint	
Primary Endpoints: Opioid utilization expressed as (oral morphine mg equivalents) during the initial 72-hour post-operative period.
 
Secondary Endpoints: Duration of opioid use Patient reported pain scores (VAS) Length of stay Reported long-term narcotic use at home Documented opioid refills Adverse events such as respiratory depression, hypoventilation, reintubation, nausea, constipation

Study Duration	3 years
Participant Duration	Four weeks

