2.2 Objectives and Purpose

The goal of this study is to determine the effectiveness of Liposomal bupivacaine at reducing opioid consumption from 24-72 hours when used along with Bupivacaine 0.5% for single shot ISB for total shoulder arthroplasty. In addition, we would also like to determine if Liposomal bupivacaine is effective at prolonging the sensory block and reducing post-operative pain in patients after TSA surgery. We would also

CONFIDENTIAL

This material is the property of the NYU School of Medicine and Langone Medical Center. Do not disclose or use except as authorized in writing by the study sponsor

like to determine how reduction in post-operative pain impacts a patient’s hospital stay in the short term. Primary outcomes measures will be opioid utilization (in morphine milligram equivalents [MME]) during a 72-hour post-operative period. Secondary outcomes include patient reported pain scores, VAS. While it is expected that the greatest benefit of Liposomal bupivacaine plus Bupivacaine 0.5% will be seen within 24-72 hours after surgery, it is possible that there will be in an overall reduction in long-term opioid use (up to 4 weeks). Secondly, function/rehabilitation, length of stay, and complications may be impacted by combined use of Liposomal bupivacaine plus Bupivacaine 0.5%.

3 Study Design and Endpoints

ARM 1: Experimental	Sample Size: 92	10 mL Bupivacaine 0.5% + 10 mL Liposomal Bupivacaine
ARM 2: Control	Sample Size: 92	20 mL Bupivacaine 0.5%

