3.1 Description of Study Design

PRE-SCREENING PHASE/CONSENTING PHASE:

Surgeons will inform eligible patients of the study during their pre-surgical visit in their office. The surgeons will use an IRB-approved recruitment flyer to help explain the study to the eligible patient. If the patient is agreeable, a member of the research team will provide further details and ask the patient to participate on day of surgery. Informed consent will be obtained on DOS when the patient is in the pre-operative holding room by an authorized research member.

BASELINE ASSESSMENTS:

After informed consent has been obtained, participants will complete a total of 3 PROMIS assessments (Upper Extremities, Pain Intensity and Global Physical Health) before undergoing their TSA surgery.

RANDOMIZATION PHASE:

Subjects scheduled to undergo TSA will be randomized to either the Bupivacaine 0.5% plus Liposomal bupivacaine Or Bupivacaine 0.5% group. Randomization of each subject will be done on day of surgery using randomization.com software to generate the assignment.

TREATMENT PHASE:

Subjects in the Bupivacaine plus Liposomal bupivacaine group will receive an interscalene nerve block with 10mL 0.5% Bupivacaine and 10mL of Liposomal bupivacaine. The control group will receive an interscalene nerve block with 20mL 0.5% Bupivacaine HCL. The anesthesiologist will NOT be blinded to what solution is being injected, as liposomal bupivacaine is a white fluid while bupivacaine is clear. All other stakeholders (patient, surgeon, other caregivers, and research staff collecting the data) will be blinded to the patient’s group assignment.

POST-OPERATIVE PHASE:

After initial recruitment, subjects’ pain will be assessed via visual analog scale (VAS) by nursing staff during the post-operative period as per standard of care. The VAS pain scores are collected and documented in the patient’s electronic medical record. Additionally, a standardized regimen of pain medication will be given to all subjects who are enrolled. The pain medications given to patients are standard of care medications and vary based on pain level. The clinical staff determines this for each patient.

CONFIDENTIAL

This material is the property of the NYU School of Medicine and Langone Medical Center. Do not disclose or use except as authorized in writing by the study sponsor

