6.2 Analysis of Endpoints

Primary Endpoints:

Opioid utilization (expressed as oral morphine mg equivalents) used during initial 24-72 hours post-operative period after surgery.

Secondary Endpoints:

CONFIDENTIAL

This material is the property of the NYU School of Medicine and Langone Medical Center. Do not disclose or use except as authorized in writing by the study sponsor

Duration of opioid use
Patient reported pain scores (VAS)
Length of stay
Progress with physical therapy
Reported long-term narcotic use at home
Discharge location: home, acute rehab or skilled nursing facility
Documented opioid refills
Adverse events such as respiratory depression, hypoventilation, reintubation, nausea, constipation

The analysis of opioid use, VAS, and PROMIS assessments will rely on a univariate analysis of variance model for mean score. This model is in the class of models commonly known as unirep-ANOVA models. It assumes that the mean score is a function of elapsed time and the treatment regimen assigned. This model considers the fact that the subject's repeated measures are correlated. The fitted model will provide statistical estimates of the mean levels, the treatment-effect differences between mean levels, the standard deviation, the intra-class correlation coefficient, 95% CIs, standard errors (SE), and statistical hypothesis tests. The estimates of means will be used to compute summary criteria such as area under the curve (AUC) for each regimen. All estimates reported will be presented their 95% CIs.

All endpoints will be evaluated as fits the data set with graphical figures such as scatter plots, box-and-whisker plots, and frequency histograms to visualize the distribution of these outcomes and their relationships to covariates and treatment assignment. When appropriate descriptive graphical and tabular methods will also be estimated and presented in a graphical figure.

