14.1 Opioid Equivalents

Notes from Lamplot (2013)

Opioid and Route	Dose (mg)	Conversion Factor
Morphine IM/IV	10	1.0
Hydromorphone IM/IV	1.67	6.0
Hydrocodone oral	30	0.3
Tramadol oral	100	0.1
Oxycodone oral	20	0.5
Vicodin 5/500 oral	6 tabs	1.7

Equianalgesic Doses of Opioids²⁸

Opioid	Oral Equianalgesic Dose (mg)
Buprenorphine	0.3
Oxymorphone	1.5
Butorphanol	2
Hydromorphone	2
Oxycodone	7
Hydrocodone	10
Morphine	10
Methadone	10-20
Tramadol	40
Propoxyphene	43-45
Codeine	80
Meperidine	100

CONFIDENTIAL

This material is the property of the NYU School of Medicine and Langone Medical Center. Do not disclose or use except as authorized in writing by the study sponsor

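### The primary endpoint is in oral morphine mg, but the only printed conversion factors are on an IM/IV morphine scale, and no rule says which conversion table applies

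*Combined protocol and SAP*

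**What the plan says.** **Endpoint.** Section 6.2 gives the primary endpoint as "Opioid utilization (expressed as oral morphine mg equivalents". The Protocol Summary uses the same unit: "Opioid utilization expressed as (oral morphine mg equivalents) during the initial 72-hour post-operative period". Section 2.2 names no route: "opioid utilization (in morphine milligram equivalents [MME".

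**Conversion.** Attachment 14.1 prints two tables.

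- The first has the only column of conversion factors. Its reference row is "Morphine IM/IV", 10 mg, factor 1.0. It also has a row for "Hydromorphone IM/IV" and rows for oral hydrocodone, tramadol, oxycodone and Vicodin. It has no row for oral morphine, which is the endpoint's own unit.
- The second is headed "Oral Equianalgesic Dose (mg". It sets oral morphine at 10 mg, gives doses without factors, and has no parenteral entry.

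No section selects a table, says how to combine them, or states a parenteral-to-oral ratio. Section 14 places the attachments outside the protocol and lets them change without an amendment.

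**What patients take.** Section 3.1 says that "a standardized regimen of pain medication will be given to all subjects who are enrolled", and then that "The pain medications given to patients are standard of care medications and vary based on pain level". Section 4.2 excludes oxycodone allergy. The home diary in 14.3 counts Percocet pills. Neither table has a Percocet row, and no section fixes the tablet strength to be used.

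**The concern.** The label on the endpoint and the scale of the printed factors differ. An analyst who applies the factor column as printed gets parenteral morphine mg and reports it as oral morphine mg.

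Neither table does the whole job. The first is in the wrong unit. The second is in the right unit but cannot convert an IM/IV dose. The obvious patch, IV drugs from the first table and oral drugs from the second, adds two different units within one patient's total.

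Section 6.2 promises means, treatment differences and 95% CIs for opioid use, and all of these carry the scale. Section 2.1 (Statistical Hypotheses) intends a conclusion about clinical relevance, which needs an mg figure that readers can interpret. Section 2 criticises the one earlier comparison for not quantifying analgesic use, so sound quantification is part of this trial's rationale. As the attachment can change without amendment, the derivation of the primary endpoint is not fixed in advance.

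**Working it through.** **Step 1. Reproduce the printed factors.** Inputs are the doses in the first table of 14.1. Formula: factor = 10 mg IM/IV morphine / listed dose.

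| Drug and route | Listed dose | 10 / dose | Printed |
|---|---|---|---|
| Morphine, IM/IV | 10 mg | 1.0 | 1.0 |
| Hydromorphone, IM/IV | 1.67 mg | 5.99 | 6.0 |
| Hydrocodone, oral | 30 mg | 0.333 | 0.3 |
| Tramadol, oral | 100 mg | 0.1 | 0.1 |
| Oxycodone, oral | 20 mg | 0.5 | 0.5 |
| Vicodin 5/500, oral | 6 tablets | 1.67 per tablet | 1.7 |

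All six reproduce after rounding to one decimal. The column is correct on its own scale, and that scale is parenteral morphine.

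**Step 2. Compare with the oral table.** Formula: oral factor = 10 mg oral morphine / listed oral dose in the second table. The comparison covers the three drugs listed by mouth in both tables.

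| Drug | Oral factor | Printed factor | Ratio |
|---|---|---|---|
| Tramadol | 10/40 = 0.25 | 0.1 | 2.5 |
| Oxycodone | 10/7 = 1.43 | 0.5 | 2.86 |
| Hydrocodone | 10/10 = 1.0 | 0.3 | 3.33 (3.0 with 0.333) |

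Example: 20 mg of oral oxycodone is 20 × 0.5 = 10 mg by the first table and 20 × 10/7 = 28.6 mg by the second.

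Hydromorphone is not a like-for-like comparison, because the first table lists it as IM/IV and the second as oral (10/2 = 5.0 per mg).

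**Step 3. Is the table choice a pure rescaling?** Only if one drug accounts for the use. The relative potencies implied by the two tables differ (gap = larger / smaller − 1):

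| Pair | First table, from doses (as printed) | Second table | Gap, from doses (as printed) |
|---|---|---|---|
| Oxycodone : hydrocodone | 1.50 (1.67) | 1.43 | 5% (17%) |
| Oxycodone : tramadol | 5.0 (5.0) | 5.71 | 14% (14%) |
| Hydrocodone : tramadol | 3.33 (3.0) | 4.0 | 20% (33%) |

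**Step 4. What mixing the tables does.** Take two illustrative patients.

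- Patient A takes 40 mg of oral oxycodone. First table: 40 × 0.5 = 20. Mixed: 40 × 10/7 = 57.1.
- Patient B takes 10 mg of IV morphine and 20 mg of oral oxycodone. First table: 10 × 1.0 + 20 × 0.5 = 20. Mixed: 10 + 28.6 = 38.6.

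They are equal on the parenteral scale but 57.1 and 38.6 when the tables are mixed, because the IV component stays in parenteral mg. Likewise, 1 mg of IM/IV hydromorphone would count 6.0 parenteral mg beside 1 mg of oral hydromorphone at 5.0 oral mg.

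**Step 5. The missing ratio.** The shared oral drugs imply 2.5 to 3.0 oral mg per parenteral mg (100/40 = 2.5; 20/7 = 2.86; 30/10 = 3.0). On that assumption, IM/IV hydromorphone would be 6.0 × 2.5 = 15 to 6.0 × 3.0 = 18 per mg on the oral scale, against 6.0 as printed. The documents state no ratio, so this is a range and not a correction.

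**The case against.** The strongest reply has four parts.

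1. **Nothing is miscalculated, and an oral scale is supplied.** An analyst who respects the stated unit would use the second table, where each factor is one division. This stands for oral drugs. It does not help with IM/IV doses, and nothing in the plan tells the analyst to pass over the only column labelled as factors.
2. **The range overstates the problem.** The 3.33 comes only from printing 0.333 as 0.3; from the doses the range is 2.5 to 3.0. Outside 14.1, the only opioid tied to patients is oxycodone (as Percocet), where the ratio is 2.86. Both statements are correct. A 2.86-fold difference in the reported mg is still large.
3. **The test is barely affected.** With one dominant oral opioid and one table throughout, the means, differences and standard errors scale together and the p-value hardly moves. The visible sample size text gives no mg effect size or SD that would depend on the scale. This stands, and it limits the severity. The mixed-table examples are hypothetical. They also depend on the window: under the 24-72 hour window in 6.2, first-day IV doses do not count, while under the 72-hour wording in the Protocol Summary and 2.2 they could.
4. **Some detail may be elsewhere.** A figure in 3.1 and the schematic in 3.2 are not visible and may describe the regimen. Tablet strength may be in the pharmacy or medical records. This is fair for the regimen and tablet strength. It does not remove the conflict between the two tables or the lack of a stated rule for choosing between them.

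**Conclusion.** The concern holds and should be fixed. The primary endpoint is labelled in one unit and its only printed factors are in another. Used as printed, the factors give oral-drug totals 2.5 to 3.3 times smaller than the oral table (2.5 to 3.0 without rounding, 2.86 for oxycodone). Means, between-arm mg differences and CIs would be too small by about the same factor and mislabelled as oral.

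The effect on the hypothesis test depends on practice that the documents do not settle. If use is almost all oral oxycodone and one table is applied throughout, the test hardly changes. If tables are mixed, or the arms use different oral drugs, the comparison itself could shift, since relative potencies differ between the tables by 5% to 20% from the listed doses and by up to 33% as printed. Section 3.1 allows drugs to vary with pain level, so this is plausible, but it is a risk and not a demonstrated bias.

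The size rests on taking both tables as printed. The documents do not show which equianalgesic values are right.

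**What to change.** Before outcome data are analysed:

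- Replace the two tables in 14.1 with one analysis conversion table on the oral morphine scale, with one unrounded factor for each drug and route.
- State one parenteral-to-oral ratio and apply it to every IM/IV dose.
- State the oxycodone mg per Percocet tablet used to convert diary counts, from pharmacy records if available.
- Add a sentence to 6.2 making this table binding for the primary endpoint, so that it cannot change outside the amendment process, and name the same unit in 2.2.

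The sponsor must reconcile the two tables and choose the values. This concerns conversion for analysis only and implies nothing about dosing.

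The cost is one table, one binding sentence in 6.2 and a unit label in 2.2. No new visits are needed and probably no new data collection, since medical and pharmacy records are already listed as sources.

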Duration of IP administration	Once during surgery
Population	184 participants scheduled for total shoulder arthroplasty (TSA)
Study Sites	NYU Langone Orthopedic Hospital
Number of participants	184
Description of Study Agent/Procedure	Injection of 20mL 0.5% Bupivacaine HCL versus 10mL Liposomal Bupivacaine plus 10mL Bupivacaine 0.5% in an Interscalene block for TSA
Reference Therapy	Reference is Bupivacaine 0.5% for Interscalene block
Key Procedures	Interscalene nerve block with Liposomal Bupivacaine + Bupivacaine 0.5%
Statistical Analysis	Intention-to-treat analysis will be performed with mean, t-tests, within and between group ANOVA and linear regression,

CONFIDENTIAL

This material is the property of the NYU School of Medicine and Langone Medical Center. Do not disclose or use except as authorized in writing by the study sponsor

1 Key Roles

Principal Investigator:

[name]

Assistant Professor of Anesthesiology
Department of Anesthesiology, Perioperative care and Pain Medicine
NYU Langone Orthopedic Hospital
NYU Langone Health
[name]
[name]
[contact]

Co-Investigators:

[name]

Professor of Anesthesiology
Department of Anesthesiology, Perioperative care and Pain Medicine
NYU Langone Orthopedic Hospital
NYU Langone Health
[name]
[name]

[name]

Assistant Professor of Orthopedic Surgery
Department of Orthopedic Surgery
NYU Langone Orthopedic Hospital
NYU Langone Health
[name]
[name]

2 Background and Specific Aims

With the growing elderly population, the number of total shoulder arthroplasty (TSA) surgeries is increasing. Nationwide, the total and partial shoulder replacements increased from about 18,000 in 2000 to over 45,000 in 2013 according to the American Academy of Orthopedic surgeons (AAOS). One of the greatest drivers of cost following TSA has been shown to be discharge disposition. Effective pain control after surgery is paramount because it facilitates rehabilitation and decreases hospital length of stay. Additionally, it may increase the likelihood of patients being discharged to their home rather than a rehabilitation or skilled nursing facility.

TSA is a procedure that is well confined within the dermatomal distribution of an interscalene brachial plexus nerve block (ISB), making it an ideal procedure to both evaluate and compare the regional potential of varying agents. Although the analgesic coverage is typically ideal, single shot injection of the long acting

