Occupational and physical therapy progress and activity goals will be reviewed. As per standard of care, motor testing of the operated shoulder and arm will be assessed during these visits. This includes: No weight bearing exercises will be performed as per surgeon's instructions and the nursing staff will continue to obtain VAS pain scores.

[figure not shown]
During the 24-72 hour post-operative period, research staff will visit the patient while they are in the hospital to obtain and verify the pain medication taken. If the patient is discharged before the 72-hour period, the research staff will give the patient a copy of a medication record diary to complete. Additionally, the staff member will call the patient within 1-2 business days to obtain the remaining opioid utilization information.

After discharge, the research staff will continue to follow up with the patient on POD 7, POD 14 and POD 30 to assess pain scores, opioid usage patterns, and functional status. The pain intensity PROMIS assessment will be administered during each phone call. Additionally, on POD 30, participants will complete the Upper Extremity PROMIS form. Research staff will verify documented opioid refills through Epic and pharmacy records.

CONFIDENTIAL

This material is the property of the NYU School of Medicine and Langone Medical Center. Do not disclose or use except as authorized in writing by the study sponsor

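### Section 6.2's unirep-ANOVA implies compound symmetry with no correction, so treatment-by-time tests and time-specific or AUC intervals for repeated opioid and pain data may be miscalibrated

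*Combined protocol and SAP*

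**What the plan says.** Section 6.2 (Analysis of Endpoints) assigns three kinds of outcome to one model: "The analysis of opioid use, VAS, and PROMIS assessments will rely on a univariate analysis of variance model for mean score". It then names the class: "This model is in the class of models commonly known as unirep-ANOVA models". The mean structure is given as "It assumes that the mean score is a function of elapsed time and the treatment regimen assigned", and the dependence between measurements is acknowledged in one sentence: "This model considers the fact that the subject's repeated measures are correlated". The quantities to be reported include "the standard deviation, the intra-class correlation coefficient, 95% CIs, standard errors (SE), and statistical hypothesis tests". The estimated means are also to be turned into AUCs, and every estimate is to carry a 95% interval.

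The same section defines the primary endpoint as "Opioid utilization (expressed as oral morphine mg equivalents) used during initial 24-72 hours post-operative period after surgery". The Statistical Analysis row of the Protocol Summary adds: "Intention-to-treat analysis will be performed with mean, t-tests, within and between group ANOVA and linear regression".

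On timing, Section 3.1 has pain scored in hospital by nursing staff, opioid use verified between 24 and 72 hours, and then: "the research staff will continue to follow up with the patient on POD 7, POD 14 and POD 30". PROMIS Pain Intensity is collected before surgery and at each call, PROMIS Upper Extremity before surgery and on POD 30, and PROMIS Global Physical Health before surgery only. Section 6.2 does not say which time points enter which model.

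**The concern.** One SD and one intra-class correlation describe a covariance matrix with the same variance at every time and the same correlation between every pair of times. The trial's own rationale makes that doubtful for opioid use and pain. Section 2 says a plain bupivacaine block lasts no longer than the first postoperative day, and Section 2.2 expects the main benefit between 24 and 72 hours. Scores should be low and similar while the block works, more variable as blocks resolve at different times, and different again during recovery. Neighbouring measurements are also likely to be more alike than distant ones.

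Two consequences follow if the assumption fails and nothing corrects for it. A treatment-by-time test refers its F ratio to too many degrees of freedom and rejects too often. An interval for the arm difference at one time, or for an AUC, takes its width from the pooled variance and correlation rather than those that apply there. These quantities bear on Aim 2, which concerns pain over the first 72 hours.

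**Working it through.** **Inputs from the documents.** 184 enrolled and 146 evaluable (Section 4.6), so 73 per arm if loss is equal. As a consistency check, with 20% loss assumed, 73 / 0.80 = 91.25, rounded up to 92 per arm, or 184. The documents give no SD, correlation, alpha or list of modelled times, so there is no covariance figure to reproduce. All SDs and correlations below are assumptions, in arbitrary units.

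**Step 1: simulated error rates.** Normal data, no treatment effect, 73 per arm, 10,000 trials per setting, tests at 5%. The Monte Carlo standard error near 5% is √(0.05 × 0.95 / 10,000) = 0.2 points. The Greenhouse-Geisser quantity is ε = tr(M)² / [(T − 1) tr(M²)], where M = CΣC and C is the centring matrix for T times; ε = 1 means sphericity holds.

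| Assumed setting | ε | Treatment-by-time, uncorrected | With Greenhouse-Geisser | Treatment main effect | Pooled-SD 95% CI coverage by time |
|---|---|---|---|---|---|
| 6 times, equal correlation 0.5, equal SDs | 1.00 | 4.9% | 4.6% | 4.8% | about 95% throughout |
| 6 times, AR(1) 0.7, equal SDs | 0.63 | 8.3% | 5.3% | 5.0% | about 95% throughout |
| 6 times, equal correlation 0.5, SDs 1.25, 1.25, 1.25, 1, 0.8, 0.8 | 0.91 | 6.0% | 5.3% | 5.1% | 91, 91, 91, 96, 99, 99% |
| 6 times, AR(1) 0.7, same SDs | 0.62 | 8.0% | 4.6% | 4.9% | 91, 91, 91, 97, 99, 99% |
| 6 times, AR(1) 0.7, SDs 2, 2, 2, 1, 0.7, 0.5 | 0.54 | 9.0% | 5.1% | 4.8% | 86, 87, 86, then nearly 100% |
| 3 times, AR(1) 0.7, SDs 0.6, 1.5, 1.2 | 0.98 | 5.5% | 5.4% | 5.3% | nearly 100, 87, 94% |
| 2 times, correlation 0.5, SDs 1.5, 1 | 1.00 | 5.3% | 5.3% | 4.9% | 90, 99% |

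A second set of runs (146 patients, equal SDs, 6,000 trials each) varied the number of times. At 4, 6 and 8 times the uncorrected treatment-by-time error was 5.6%, 6.5%, 7.4% with AR(1) 0.5; 6.2%, 7.7%, 8.6% with 0.7; and 6.8%, 8.3%, 9.9% with 0.8.

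**Step 2: why single-time intervals fail.** In large samples the pooled variance is the average of the time-specific ones, so coverage at time t = 2Φ(1.96 √(average variance / variance at t)) − 1.

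- Six times, SDs 1, 2, 2.5, 2.5, 2, 1.5: average variance = (1 + 4 + 6.25 + 6.25 + 4 + 2.25)/6 = 3.958. Where the SD is 2.5: 1.96 × √(3.958/6.25) = 1.56, coverage 88%.
- Four times within 72 h only, SDs 1, 2, 2.5, 2.5: average variance = 17.5/4 = 4.375. Where the SD is 2.5: 1.96 × √(4.375/6.25) = 1.64, coverage 90%.

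The interval problem therefore does not need a single fit out to POD 30.

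**Step 3: AUC.** Take a 24-72 h AUC from values at 24, 48 and 72 h with trapezoid weights 0.5, 1, 0.5, AR(1) 0.7, and SDs 2, 2.5, 2.5 at those times.

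- True variance = 0.25 × 4 + 6.25 + 0.25 × 6.25 + 2(0.5 × 3.5 + 0.5 × 4.375 + 0.25 × 2.45) = 17.91.
- In the six-time fit, the pooled model has variance 3.958 and average correlation 0.468. It gives 3.958 × (1.5 + 2.5 × 0.468) = 10.57.
- Coverage = 2Φ(1.96 √(10.57/17.91)) − 1 = 87%. The same calculation gives 90% for the four-time fit.
- With equal SDs, unequal correlation alone gives 3.145 (true) against 1.5 + 2.5 × 0.476 = 2.69 (model), so coverage is 93%.

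**Step 4: what is not touched.** The main-effect test compares patient means and needs no sphericity; it stayed between 4.8% and 5.3% in every setting. A t-test on one total per patient gave 4.8% in 50,000 simulated trials.

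**The case against.** The strongest reply is that little of the confirmatory analysis is exposed. The primary endpoint is an amount over one window. Analysed as one total per patient, for which the Protocol Summary's t-tests would serve, it has no within-patient covariance to misspecify. Section 6.2 names no treatment-by-time test. The main-effect test holds its level, and single-time intervals are correct when SDs are equal, even under AR(1) correlation. All of this stands, with one qualification: Section 6.2 sends opioid use to the repeated-measures model without saying whether it enters as one total or as several values.

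A reader might also infer more than the documents support:

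- **That all the plan's tests and intervals are wrong.** Step 4 rules this out. PROMIS Upper Extremity has two time points, so its treatment-by-time test meets sphericity automatically, although a pooled-SD interval could still miss. PROMIS Global Physical Health has no follow-up value.
- **That everything from the first hours to POD 30 goes into one fit.** No section says so, and the outcomes have different schedules. PROMIS Pain Intensity has no first-hours values.
- **That the 24-72 h intervals are necessarily too narrow.** This depends on where the spread is largest, which the documents do not show.
- **That incomplete patients will be dropped from the repeated-measures analysis.** A classical unirep-ANOVA would need complete data, but a random-intercept fit also yields one SD and one intra-class correlation and accepts incomplete records. The text does not settle which is meant, and no missing-data scenario was simulated.

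What survives the reply is that Section 6.2 commits to a specific covariance, the trial's rationale makes it doubtful for opioid use and pain, and no check or correction is named.

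**Conclusion.** The concern holds for treatment-by-time tests, single-time intervals and AUC intervals on repeated opioid and pain data. In most of the assumed settings that depart from compound symmetry, the uncorrected treatment-by-time error was about 6% to 9%. It was as low as 5.5% with three times and as high as 9.9% with eight. Pooled-SD intervals covered about 86% to 91% where spread was high and were too wide where it was low; AUC intervals covered 87% to 90% in the unequal-spread cases worked above. Greenhouse-Geisser brought the interaction test back to 4.6% to 5.4% but does nothing for the intervals.

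These sizes rest on normal data, 73 per arm, and SDs and correlations that I chose. They show what could happen, not what will. The point does not undermine the treatment main effect or a primary total analysed once per patient. It is a cheap improvement to the analysis wording.

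**What to change.** 1. State in Section 6.2 that the primary 24-72 h MME is analysed as one total per patient.
2. For repeated opioid use, VAS and PROMIS Pain Intensity, list the time points or windows for each outcome. In-hospital VAS needs this most, because it is taken under standard care with no schedule given. Then replace unirep-ANOVA by a mixed model with categorical time, treatment, treatment-by-time, unstructured covariance, Kenward-Roger degrees of freedom and all available data. Adjust for baseline only where a baseline value is collected, which Section 3.1 provides for PROMIS. Derive the time-specific differences and any AUC, with their intervals, from this model.
3. If unirep-ANOVA is kept, specify Greenhouse-Geisser corrected tests and time-specific standard errors. An AUC interval should then also use the estimated covariances between times.

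The cost is analysis-plan wording and standard software, plus more covariance parameters: with six times, 6 × 7 / 2 = 21 instead of 2. That is manageable with about 146 evaluable patients, provided the windows are defined first and kept few.
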